8. STUDY PROCEDURES/EVALUATIONS

8.1. Clinical evaluations

8.1.1. Demographics

Race, ethnicity, age (year of birth only), and gender will be captured as demographic data at screening.

8.1.2. Medical History & Concomitant Medication Review

Prior and concomitant medication as well as significant medical history (including all ocular history) will be reviewed and recorded in the eCRF.

This information will comprise (and be updated throughout the study):

- Documentation of presenting complaints and history
- All current and prior ocular medical and surgical history
- All current and prior significant general medical and surgical history
- Pertinent family (e.g., related parents and children) and social history
- Current medication use (ocular and other) and those used in past 90 days
- Any drug allergy or contraindication to steroids

8.1.3. Vital Signs

Vital signs including heart rate, temperature, and blood pressure will be measured. Blood pressure (systolic and diastolic) is to be measured in triplicate after five minutes rest in a sitting position for the screening assessment only. The same method should be used throughout the study. Pulse will be assessed as a single measurement.

8.1.4. Pregnancy Test

Females of child-bearing potential are defined as those who have experienced menarche in the past 12 months and do not meet the criteria for women not of child-bearing potential. Women not of child-bearing potential are females who are permanently sterile (e.g., bilateral tubal ligation, hysterectomy, or bilateral oophorectomy) or post-menopausal. Post-menopausal is defined as 12 consecutive months with no menses without an alternative medical cause.

Females of childbearing potential will undergo urine pregnancy testing at Visit 1 (screening). In case the screening visit and the dosing day is more than 14 days apart, a urine pregnancy test will be repeated before surgery to exclude an early pregnancy.

8.2. Laboratory Evaluations

8.2.1. Clinical Laboratory Evaluations

The anticipated volume of blood samples collected during the study from each subject will not exceed 250 mL (over approximately one year). Any remains from the safety laboratory samples will be disposed of after analyses.

Blood samples for analysis of clinical chemistry and haematology variables will be collected at all specified visits and sent to the central laboratory.

The following safety laboratory variables will be assessed:

Table 5: Laboratory Parameters

Panel	Parameter	Panel	Parameter
Biochemistry	Albumin	Haematology	Haemoglobin
	Alkaline Phosphatase		Haematocrit
	Alanine Aminotransferase		Mean Corpuscular Haemoglobin
	Aspartate Aminotransferase		Mean Corpuscular Haemoglobin Concentration
	Bicarbonate		Erythrocytes
	Bilirubin (Direct)		Leucocytes
	Bilirubin (Indirect)		Differential Count:
	Bilirubin (Total)		Basophils
	Calcium		Eosinophils
	Chloride		Lymphocytes
	Creatine Kinase		Monocytes
	Creatinine		Neutrophils
	C-Reactive Protein		Large Unstained Cells
	Gamma Glutamyl Transferase		Platelets
	Globulin		
	Glucose (Random)		
	Lactate Dehydrogenase		
	Magnesium		
	Phosphate		
	Potassium		
	Protein Total		
	Sodium		
	Blood Urea Nitrogen		
	Estimated glomerular filtration rate (using CKD-EPI formula)		

8.2.2. Non-standard Assays

Serum CFI Levels

Serum CFI levels will be evaluated using a validated enzyme-linked immunosorbent assay.

Genetic Testing for Complement Genotypes Associated with AMD

Subjects entered into the study must have genotyping performed by a Sponsor-approved laboratory, either through participation in a previous Sponsor study, or during the FOCUS screening period. [REDACTED]

Region	Percentage (%)
North East	15.2
North West	14.8
Scotland	14.5
Wales	14.2
England	13.8
Midlands	13.5
South East	13.2
South West	12.8
East of England	12.5
London	12.2

8.2.3. Ophthalmic Procedures

Standard Ophthalmic Examination

Ophthalmological examinations in both eyes will be performed as follows: anterior segment examination including ocular inflammation assessment via slit lamp

biomicroscopy, IOP via Goldmann applanation tonometry, posterior segment and fundus examination via dilated indirect ophthalmoscopy.

Slit lamp will be conducted on both eyes. The eyelids, cornea, conjunctiva, anterior chamber, iris/pupil and lens should be evaluated. Findings will be graded as normal, abnormal non-clinically significant, or abnormal clinically significant. Cataract will be graded using the AREDS clinical lens grading system (see Section 26.3). Intraocular pressure will be assessed in both eyes with a tonometer.

Dilated indirect ophthalmoscopy will assess the vitreous, macula, choroid, optic nerve, retina and cup- to-disc ratio of both eyes. Findings will be graded as normal, abnormal non-clinically significant, or abnormal clinically significant. Indirect ophthalmoscopy will be performed per the Schedule of Assessments.

Measurement of Geographic Atrophy

GA area is measured by FAF.

Prior to study start, sites will be qualified by a central reader to ensure fundus images fulfil the appropriate quality requirements. For consistency and to reduce variability, all images will be taken according to a study specific imaging protocol provided to all sites by the reading centre; all images will be reviewed and quantified by a central reader.

The study specific imaging protocol is part of the GT005-01 Photographer Certification, Imaging, & Export Manual.

Fundus Autofluorescence

Fundus autofluorescence is a non-invasive retinal imaging modality used in clinical practice to provide a density map of lipofuscin, the predominant ocular fluorophore, in the RPE.

Autofluorescence images of the fundus of both eyes will be obtained using the clinical site's preferred ophthalmic imaging camera. Additional imaging of pertinent retinal regions can be performed at the discretion of the Investigator.

Detailed instructions are part of the GT005-01 Photographer Certification, Imaging, & Export Manual.

Colour Fundus Photography

Colour images of the fundus of both eyes will be obtained using the clinical site's preferred ophthalmic imaging camera. Additional imaging of pertinent retinal regions can be performed at the discretion of the Investigator.

Detailed instructions are part of the GT005-01 Photographer Certification, Imaging, & Export Manual.

Optical Coherence Tomography (Macula [REDACTED])

Optical coherence tomography is a method of using low-coherence interferometry to determine the echo time delay and magnitude of backscattered light reflected off an object of interest. This method can be used to scan through the layers of a structured tissue sample such as the retina with very high axial resolution (3 to 15 µm), providing images demonstrating three-dimensional structure. Because of the unique optically clear pathway through the eye, OCT has been used most extensively for imaging disorders affecting the retina.

A series of horizontal raster scans centred on the fovea of each eye will be obtained with Heidelberg Spectralis (specific setting will be defined in the GT005-01 Photographer Certification, Imaging, & Export Manual).

Additional OCT imaging of pertinent retinal regions of the treated eye may be performed at the discretion of the Investigator.

Detailed instructions are part of the GT005-01 Photographer Certification, Imaging, & Export Manual.

Optical Coherence Tomography-A

Optical coherence tomography-A allows for non-invasive evaluation of retinal and choroidal vascular abnormalities that is useful as a diagnostic tool for Investigators to identify CNV which is an eligibility exclusion criterion. OCT-A may be performed as clinically indicated during the course of the study, for example, if a subject converts to wet AMD.

If OCT-A is not available, other imaging modalities as described in the Central Imaging Manual may be utilised to assess for CNV.

Detailed instructions are part of the GT005-01 Photographer Certification, Imaging, & Export Manual.

Fluorescein Angiography

A contrast medium (Sodium Fluorescein) is injected into a vein in the subject's arm. The dye travels quickly through the circulatory system and is photographed in black and white as it travels through the eye. The same camera used for fundus photography is employed in this procedure. Two filters are used to limit the image to the colour of light being emitted from the fluorescent dye.

The normal progression of dye is interrupted by diseases of the choroid, retina, and retinal vasculature.

Fluorescein angiography should be performed in the event, that the OCT/OCT-A images are inconclusive in order to rule out the presence of CNV. Fluorescein angiography may also be performed prior to the OCT/OCT-A result being available, however, this is not mandatory.

Detailed instructions are part of the GT005-01 Photographer Certification, Imaging, & Export Manual.

Microperimetry

Microperimetry, sometimes called fundus related perimetry, is a type of visual field test used to create a "retinal sensitivity map" of the quantity of light perceived in specific parts of the retina in people who have lost the ability to fixate on an object or light source.

The combination of subjective (sensitivity map) and objective (retinography) data will be unified on a microperimetry map, allowing analysis of the retinal function before and after treatment.

As microperimetry is an exploratory assessment it will be included at those sites who have the capability in this study; it is acknowledged that some subjects may not be able to perform this test because of limited ability to fixate.

Detailed instructions are part of the GT005-01 Photographer Certification, Imaging, & Export Manual.

Visual Acuity: BCVA and LLVA using the ETDRS chart

The BCVA of each eye will be performed by obtaining the subject's manifest refraction and using the BCVA ETDRS methodology at 4 meters or 1 meter, or level of count fingers, hand motion or light perception.

Low luminance visual acuity should be performed immediately after BCVA and involves placing a 2.0-log-unit neutral density filter over the front of each eye.

Detailed instructions are part of the Investigator Site File.

Additional functional assessments (microperimetry or standard perimetry)

Additional microperimetry/perimetry should be collected either at the next scheduled visit or at an unscheduled visit if there is no upcoming planned study visit. If a standard perimeter is not available at the site, the Sponsor will assist with arranging transport of the subject to another location to perform the assessment. This additional safety assessment should be acquired at all future study visits (refer to the Central Imaging Manual for specific instructions for functional assessment collection).

8.2.4. Historical FAF and OCT images

If available, historical FAF and/or OCT images obtained within 1 year prior to enrolment will be reviewed by the Central Reading Centre to assess GA lesion size, with the purpose to obtain pre-treatment information on GA growth, to explore the natural history of disease progression.

Enrolled subjects will be asked if they are willing to consent to have historical FAF and/or OCT images that were obtained within 1 year prior to enrolment, if available, provided to the sponsor. This is optional and requires additional consent; the Investigator or designee will explain that the subject is under no obligation to provide this consent. If informed consent is given by a subject, the images will be provided to the Central Reading Centre and the historical lesion size will be measured and recorded.

Detailed instructions are part of the GT005-01 Photographer Certification, Imaging, & Export Manual.

8.3. Contraceptive Requirements

Each subject will be reminded to use two forms of contraception (one of which being a barrier method) for 90 days for men and women of child-bearing potential.

Male subjects

Male subjects whose female partner(s) is (are) pregnant must use a condom from the time of the first administration of treatment or study medication until three months (90 days) following administration of the last treatment or dose of study medication.

If the subject has undergone surgical sterilisation (vasectomy with documentation of azoospermia) a condom must be used.

Male subjects must use acceptable methods of contraception if the male subject's partner could become pregnant from the time of the first administration of treatment or study medication until three months following administration of the last treatment or dose of study medication. The acceptable methods of contraception are as follows:

- Condom and occlusive cap (diaphragm or cervical/vault caps) with spermicidal foam/gel/film/cream/suppository
- Surgical sterilisation (vasectomy with documentation of azoospermia) and a barrier method (condom or occlusive cap (diaphragm or cervical/vault caps) used with spermicidal foam/gel/film/cream/suppository)
- The female partner uses oral contraceptives (combination oestrogen/progesterone pills), injectable progesterone or subdermal implants and a barrier method (condom or occlusive cap (diaphragm or cervical/vault caps) used with spermicidal foam/gel/film/cream/suppository)
- The female partner has undergone documented tubal ligation (female sterilisation). In addition, a barrier method (condom or occlusive cap (diaphragm or cervical/vault caps) used with spermicidal foam/gel/film/cream/suppository) must be used
- The female partner has undergone documented placement of an intrauterine device or intrauterine system and the use of a barrier method (condom or occlusive cap (diaphragm or cervical/vault caps) used with spermicidal foam/gel/film/cream/suppository)
- True abstinence when this is in line with the preferred and usual lifestyle of the subject. *Periodic abstinence (e.g., calendar, ovulation, symptothermal, post-*

ovulation methods) and withdrawal are not acceptable methods of contraception

Female subjects

Female subjects of childbearing potential must use medically acceptable methods of contraception from the time of the first administration of treatment or study medication until three months (90 days) following administration of the last treatment or dose of study medication for women of childbearing potential.

Acceptable methods include:

- A documented placement of an intrauterine device or intrauterine device and the use of a barrier method (condom or occlusive cap (diaphragm or cervical/vault caps) used with spermicidal foam/gel/film/cream/suppository)
- Documented tubal ligation (female sterilisation). In addition, a barrier method (condom or occlusive cap (diaphragm or cervical/vault caps) used with spermicidal foam/gel/film/cream/suppository) should also be used
- Double barrier method: condom and occlusive cap (diaphragm or cervical/vault caps) with spermicidal foam/gel/film/cream/suppository
- Oral contraceptives (combination oestrogen/progesterone pills), injectable progesterone or subdermal implants and the use of a barrier method (condom or occlusive cap (diaphragm or cervical/vault caps) used with spermicidal foam/gel/film/cream/suppository)
- True abstinence when this is in line with the preferred and usual lifestyle of the subject. *Periodic abstinence (e.g., calendar, ovulation, symptothermal, post-ovulation methods) and withdrawal are not acceptable methods of contraception*

9. ADVERSE EVENT REPORTING

9.1. Definitions

All AEs will be captured from the time the subject provides written informed consent and monitored throughout the study.

Adverse Event: Untoward medical occurrence in a subject administered a pharmaceutical product and that does not necessarily have a causal relationship with this treatment.

An AE can therefore be any unfavourable and unintended sign (including laboratory abnormal finding), system or disease temporally associated with the use of the medicinal product, whether or not considered as related to GT005.

Adverse Drug Reaction: Untoward and unintended responses to GT005 related to any dose administered.

All AEs judged by either the reporting Investigator or the Sponsor as having a reasonable causal relationship to a medicinal product qualify as adverse reactions. The expression “reasonable causal relationship” means to convey in general that there are facts or evidence meant to suggest a causal relationship.

Serious Adverse Event: Untoward medical occurrence or effect that at any dose falls in one or more of the following categories:

- Results in death
- Is life-threatening
- Requires hospitalisation or prolongation of existing inpatient hospitalisation. Hospitalisation refers to a situation whereby an AE is associated with unplanned overnight admission into hospital.
- Results in persistent or significant disability or incapacity
- Is a congenital anomaly or birth defect
- Is a medically significant AE

Adverse Events of Special Interest (AESI): An AESI (serious or non-serious) is one of scientific and medical concern specific to the Sponsor’s product or program, for which ongoing monitoring and rapid communication by the Investigator to the Sponsor can be appropriate. [REDACTED]

[REDACTED]

[REDACTED]

[REDACTED]

[REDACTED]

[REDACTED]

It is anticipated that there may be transient decreases to visual acuity related to the subretinal injection surgical procedure. A transient visual loss may be observed in the first days post-surgery due to bleb-related foveal detachment, if performed. Transient surgery-related events of decreases in visual acuity are defined as decreases occurring in close temporal association (within <24 hours) with the surgical administration of the study medication, and which are resolving at Week 1 (Visit 3) post-surgery.

Additionally, there is a known risk of cataract associated with any vitrectomy procedure. A published review from [Feng 2014] shows cataract to be common following pars plana vitrectomy with about 40% of patients requiring a cataract extraction over the following 2 years.

These do not require reporting as AESIs.

Device Specific Adverse Events:

Serious injury means an injury or illness that:

1. Is life-threatening,
2. Results in permanent impairment of a body function or permanent damage to a body structure, or
3. Necessitates medical or surgical intervention to preclude permanent impairment of a body function or permanent damage to a body structure. Permanent means irreversible impairment or damage to a body structure or function, excluding trivial impairment or damage.

For the reporting purposes of this study, a serious injury related to the device is considered an SAE.

9.2. Expectedness

An expected adverse reaction is where the nature or severity of the AE is consistent with the applicable product information (IB for an unapproved investigational product or SmPC or approved Package Insert for an authorised product), otherwise it is considered unexpected.

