9.7. Recording Adverse Events

It is the responsibility of the Investigator to collect all AEs (both serious and non-serious).

All AEs occurring during the study must be documented on the appropriate section of the eCRF.

If an AE is considered serious, it must also be recorded on the Serious Adverse Event Form provided separately.

9.8. Reporting Serious Adverse Events and Adverse Events of Special Interest to the Sponsor

All AESIs and SAEs occurring from informed consent through to the long-term follow-up section of the study, or if the subject is not taking part in the long-term follow-up part of the study, until resolution of the event will be reported immediately (within 24 hours) by the Investigator, Contract Research Organisation (CRO) and/or Sponsor to the [REDACTED] Safety team, regardless of causal relationship. The applicable form (electronic data capture or back-up form) must be filled in by a member of the research team and kept in the Investigator site file.

All SAEs/AESIs must be reported in the eCRF. Alternatively, if the eCRF cannot be accessed, please contact [REDACTED] by telephone, fax or email:

[REDACTED] **SAE hotline – United States:**

Telephone: [REDACTED]

Fax: [REDACTED]

e-mail: [REDACTED]

OR

[REDACTED] **SAE hotline – Europe:**

Telephone: [REDACTED]

Fax: [REDACTED]

e-mail: [REDACTED]

Where the Investigator requires advice regarding the handling of SAEs/AESIs the contact in case of emergency is:

[REDACTED], ***dial 3 (United States)***

OR

[REDACTED] ***(Europe)***

A pregnancy is not considered to be an AE or SAE; however, it must be reported to Medpace Clinical Safety within 24 hours of knowledge of the event. Medpace Clinical Safety will then provide the Investigator/site the Exposure In Utero (EIU) form for completion. The Investigator/site must complete the EIU form and fax/email it back to Medpace Clinical Safety. The pregnancy should be followed until the outcome of the pregnancy, whenever possible. Once the outcome of the pregnancy is known, the follow-up EIU form should be completed and faxed/mailed to [REDACTED] Clinical Safety.

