Gyroscope Therapeutics will report all relevant safety information about suspected unexpected serious adverse reactions (SUSARs) (and any new safety information that would adversely affect the safety of subjects or the conduct of the study) for the product under investigation to the Competent Authorities, Institutional Review Boards (IRBs)/Research Ethics Committee (RECs), Investigators and DSMB for the duration of the study as required by country-specific regulations.

In addition, any new safety information that would adversely affect the safety of subjects or the conduct of the study will be reported by Gyroscope to the Competent Authorities, Research Ethics Committees (RECs), DSMB and Investigators. If the study is to be suspended as a result of a SUSAR, or due to any urgent safety measure taken, Competent Authorities and RECs will be notified as soon as possible and within three days of the decision.

For study centres in the United States, Investigational New Drug safety reports will be submitted directly to the Investigators. It is the Investigators' responsibility to notify their IRBs/RECs in a timely manner. Gyroscope will submit Safety Reports to the applicable Competent Authorities and IRBs/RECs as required by country-specific regulations.

[REDACTED]

[REDACTED]

[REDACTED]

[REDACTED]

[REDACTED]

[REDACTED]

[REDACTED]

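### Protocol Section 9.2 lets one match, nature or severity, make a reaction expected, so a listed reaction in a worse form than listed falls outside the protocol's SUSAR definition

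*Protocol*

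**What the plan says.** Protocol Section 9.2 (Expectedness) defines the term in one sentence: "An expected adverse reaction is where the nature or severity of the AE is consistent with the applicable product information". The reference document is the "IB for an unapproved investigational product or SmPC or approved Package Insert for an authorised product"; for GT005, which is unapproved, that means the Investigator's Brochure. The sentence closes with "otherwise it is considered unexpected", so the unexpected class is simply what remains.

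Protocol Section 9.8 uses that class. The sponsor "will report all relevant safety information about suspected unexpected serious adverse reactions (SUSARs") to the Competent Authorities, the IRBs/RECs, the investigators and the DSMB, "for the duration of the study as required by country-specific regulations". The same section separately says that "any new safety information that would adversely affect the safety of subjects or the conduct of the study will be reported by Gyroscope". Before any of this, AESIs and SAEs of any cause "will be reported immediately (within 24 hours) by the Investigator, Contract Research Organisation (CRO) and/or Sponsor" to the safety team.

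Protocol Section 9.3 has the investigator grade each event's maximum intensity on a three-step scale. Severity is thus recorded separately from the nature of the event. The SAP does not define or use expectedness.

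**The concern.** The connector is wrong for the term being defined. Nature or severity suits a definition of unexpected: a reaction is unexpected if either attribute departs from the product information. Placed in a definition of expected, the same word reverses the effect. One agreement is enough to be expected, and both attributes must disagree before the reaction is unexpected. This is probably a drafting slip, but it is the current operative text.

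The case at stake is a serious reaction, suspected to be related, of a type the brochure already lists but in a worse form than it describes. That is a signal an outside reviewer would want promptly in a first-in-human study of a product that cannot be removed once injected (Protocol Section 4.4). Under the written rule the reaction is expected, so it does not meet the protocol's own condition for a SUSAR report.

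**Working it through.** No numerical input is involved and there is no plan figure to reproduce. The check sets Sections 9.2 and 9.8 side by side and works through the cases.

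**Step 1: the rule as written (Section 9.2).** Let N mean that the nature is consistent with the product information, and S that the severity is consistent.

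- As written: expected = N or S; unexpected = neither N nor S.
- Both required: expected = N and S; unexpected = at least one fails.

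**Step 2: the four combinations.**

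| Nature consistent | Severity consistent | As written | Both required |
|---|---|---|---|
| Yes | Yes | Expected | Expected |
| Yes | No | Expected | Unexpected |
| No | Yes | Expected | Unexpected |
| No | No | Unexpected | Unexpected |

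The written rule calls 3 of 4 expected; requiring both calls 1 of 4 expected. The class changes in 3 − 1 = 2 combinations.

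**Step 3: which of the two changes is real.** The second row is a listed reaction in a worse form than listed. It can plainly occur, because severity is graded apart from nature (Section 9.3). The third row is strained: if the brochure does not list a reaction, it states no severity for that reaction to match. The supportable effect is therefore the second row alone.

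**Step 4: the consequence (Section 9.8).** A SUSAR must be suspected to be related, serious and unexpected. A second-row event that is serious and related meets the first two conditions and, under Section 9.2, fails the third. It is outside the SUSAR route as the protocol defines it.

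**Step 5: whether another rule overrides this.**

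| Provision | Depends on expectedness? | Corrects Section 9.2? |
|---|---|---|
| 24-hour SAE/AESI reporting (Section 9.8) | No | No; it reaches the safety team only |
| New safety information (Section 9.8) | No | No; a separate route that turns on a judgement of impact |
| Country-specific regulations (Section 9.8) | Not stated | No; they may govern practice, but the protocol gives no other definition |
| DSMB review of all safety data (Section 24.1) | No | No |
| Stopping rules, related toxicity within five weeks of treatment (Section 24.1) | No | No |

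Each provision lowers the chance that a serious signal goes unseen. None changes the classification.

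**The case against.** The strongest reply is that little turns on this sentence. Every SAE reaches the safety team within 24 hours whatever its cause. The duty to report new safety information is mandatory in its wording, names authorities, ethics committees, investigators and the DSMB, and does not pass through expectedness; a markedly worse form of a known reaction could well fall under it. Reporting is tied to country-specific regulations. The DSMB reviews all safety data and may meet ad hoc, and its stopping rules turn on lasting loss of vision, threat to life, or harm outweighing benefit. The adverse-event summaries in SAP Section 3.9.1 do not use expectedness.

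All of that stands as a limit on impact, and it rules out several stronger readings that a reader might infer:

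- **That such events go unreported.** The documents show what the protocol's definition would produce, not what was done. Regulations or the new-safety-information clause may bring the report about.
- **That new types of reaction are lost, or that two of three discordant cases are misclassified.** The two-of-three figure counts rows of a logic table, not events, and one of those rows is the strained one.
- **That particular risks named in Protocol Section 1.6, such as intraocular inflammation or worsening of vision, are affected.** The reference is the brochure, which is not among the documents. Whether it lists them, and at what severity, cannot be checked.
- **That past SAEs were wrongly classified.** Nothing in the documents shows this.

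What the reply does not do is make the sentence right. The safeguards work alongside the definition. The new-safety-information clause rests on a judgement that an expected label may weigh against. The stopping rules cover toxicity evident within five weeks of treatment, while follow-up runs to Week 240. If regulations lead the sponsor to classify correctly, the protocol then disagrees with practice.

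**Conclusion.** Section 9.2 is wrong as written. Taken literally, a related serious reaction of a listed type but of greater severity than listed is classed as expected and falls outside the protocol's SUSAR route. That follows directly from Sections 9.2 and 9.8 and rests on two assumptions: that the sentence is applied as worded, and that the brochure describes the severity of at least some listed reactions.

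The size cannot be put as a number of events. It is one practically meaningful class of event, in a study of about 65 subjects, with other reporting and review routes still in place. No endpoint, analysis set, dose-escalation rule or stopping rule depends on it. It is worth correcting because it bears on participant protection, safety is the primary objective, and the correction is small.

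**What to change.** Replace the sentence in Protocol Section 9.2 with:

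*An adverse reaction is expected only if both its nature and its severity are consistent with the applicable product information; if either is not consistent, it is unexpected.*

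As a precaution, re-check the expectedness of related SAEs already classified, looking for listed reactions whose severity exceeded the listing. This does not presume that an error was made.

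The cost is one sentence of protocol text, a short review in a study of this size, and possibly a few more expedited reports. The change concerns reporting only and leaves treatment, visits and analyses as they are.
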